# 3.2 Power considerations for key secondary analysis

While key secondary efficacy endpoints will be further tested in a hierarchical order if both null hypothesis in the primary analysis are rejected, no power evaluation was performed for secondary analysis given the anticipated diminishing power after two primary hypothesis tests.

# 4 Change to protocol specified analyses

Analysis details, as well as editorial and semantic changes where appropriate, are implemented for different sections without altering the planned methods of analysis. The following significant changes from protocol are implemented in this SAP.

- 4.1 For the estimand definition in Section 2.5, one intercurrent event "Early discontinuation of study treatment or withdrawal from study before week 48 visit" is added to cover the two separately listed events "early stop of study treatment before week 24" and "premature study discontinuation before week 24" in original protocol. This updated intercurrent event also include the situation of early stop of study treatment or withdrawal from study after week 24 but before week 48. Such situation was implicitly considered as an intercurrent event, addressed with imputation but not explicitly listed as an intercurrent event in study protocol. This update does not change the primary analysis planned in the study protocol.
- 4.2 For the intercurrent events associated with prohibited medications, any alcohol usage more than what is permitted in the protocol, initiation of other T2DM or lipid lowering medication (e.g. GLP-1 modulator) or initiation of other treatment being evaluated or approved for NASH are also included as intercurrent event. This change is in consideration of newly identified interventions that may confound study treatment effect but not listed in the current version of study protocol.
- 4.3 Key secondary analyses are added into the hierarchical testing procedure after the primary analysis (Section 2.6). This change enables potentially more statistical evidence accumulation without affecting the primary analysis.
- 4.4 Formulation of the null and alternative hypotheses in Section 2.5 and 2.6 are updated based on odds ratio instead of difference as the test statistics. This update does not change the analysis method originally planned in protocol but to keep consistent with the actual test statistics that will be used for the hypothesis tests.
- 4.5 P-values will not be provided if formal hypothesis test is not performed. This change is implemented to avoid potential confusions or misinterpretation of the results.
- 4.6 For secondary **analysis** analysis using repeated measurement ANCOVA model, inclusion of interaction between time (visit) and treatment are explicitly clarified. This change is to ensure consistent implementation of the analysis to account for the possibility that treatment effects change over time.
- 4.7 Additional sensitivity analysis for the primary endpoint based on CMH test is added (Section 2.5.4), given its robustness against risk of potential misassumption for the logistic regression for primary analysis. This change is implemented also in response to FDA comments.
- 4.8 Multiple imputations will be performed based on FCS with logistic regression instead of discriminant function (Section 2.5.3). This change is implemented for the convenience of including dichotomous predictors in the imputer's model.

Novartis SAP	For business use only	Page 35 CLJN452D12201C
4.9	Multiple imputations will be implemented by excluding treatment imputer's model instead of performing MI separately within ea (Section $2.5.3$ ). This change helps to reduce the computational implementation and enables more complete cases for the MI.	ach treatment group
4.10		
4.11	Demographics and baseline characteristics summary will be on $2.3$ ). This change is implemented in the spirit of lean SAP beca difference between SAF and FAS is expected.	•
4.12	Listing of safety data pre- or post treatment will not be product implemented in the spirit of lean SAP and such listings are cor- for the objectives of the study. To support data review and wri- informal listings can be used.	nsidered not essential

# SAP

Novartis

# 5 Appendix

# 5.1 Imputation rules

#### 5.1.1 First and last dose dates of study treatment

Partially missing start or stop date of study treatment is not expected given the eCRF design.

Missing first dose date for patients with known exposure to study treatment will be resolved through data queries.

For patients with non-missing first dose date, a missing last dose date (e.g. due to lost to follow up) will be imputed with patient's first dose date or the last known exposure to study treatment according to change in dosing CRF page, whichever is later.

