
After the 3-capsule supply is depleted, participants will take 1-capsule of 140 µg tropifexor or matching placebo daily as described in Table 6-6. No change is made to licogliflozin dosing.

Novartis Amended Protocol Version 02 (Clean) Confidential

Table 6-6	Dosing with single capsule (140 μg) tropifexor supply						
Treatment Arm	Tropifexor (LJN452) 140µg capsule	Tropifexor (LJN452) Placebo capsul e	Licogliflozin (LIK066) 10mg tablet	Licogliflozin (LIK066) Placebo tablet	Frequency		
Arm A Combo Tropifexor (LJN45 2) 140 μg & Licogliflozin (LIK06 6) 30 mg	1	0	3	0	Daily		
Arm B Mono Tropifexor (LJN45 2) 140 μg	1	0	0	3	Daily		
Arm C Mono Licogliflozin (LIK06 6) 30 mg	0	3	3	0	Daily		
Arm D Placebo	0	3	0	3	Daily		

IMPORTANT: Please ensure that the date of the change, and the number of capsules (from 3 capsule to 1 capsule) is accurately captured in the eCRF Change in Dosing log for each participant.

Dosing recommendations:

1. Participants should take 3 Tablets from the blister pack (licogliflozin or matching placebo) & 1 or 3 Capsules (tropifexor or matching placebo) depending on current supply close to the evening meal; either just prior to (within 5 minutes) consuming the evening meal, or no more than 30 minutes after consuming the evening meal, at about the same time each day. Participants directed to take 3 capsules must be reminded that one capsule is to be taken from each of the 3 tropifexor/placebo bottles provided. At Baseline and week 4 the dose will be taken in the morning at the clinic close to a meal instead of in the evening.

Confidential

- 4. Participants should be instructed to swallow the capsules and tablets whole and not to chew them.
- 5. If vomiting or diarrhea occurs during the course of treatment, no re-dosing of the participant is allowed before the next scheduled dose.
- 6. If a dose is missed and not remembered the same day, it should not be made up on a subsequent day.

All kits of study treatment assigned by the IRT will be recorded/databased in the IRT system.

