8.2.7 Treatment exposure and compliance

All doses of study treatment administration will be recorded on the appropriate eCRF page. Compliance will be assessed by means of site and participant-specific drug accountability by Novartis study personnel during the site monitoring visits using medication pack numbers, Drug Label Form information and information collected by IRT.

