#### 2.1.1 General definitions

**Study treatment** in this SAP refers to the investigational regimens, i.e. the combination of tropifexor (LJN452) 140  $\mu$ g and licogliflozin (LIK066) 30 mg, or each of them as monotherapies combined with matching placebo for the other. For simplicity hereafter, "LJN452" and "LIK066" in this SAP refer to the two specific dose strength of LJN452 140  $\mu$ g and LIK066 30 mg unless otherwise specified.

**Date of first study treatment ("first dose date" or "FDDT" )** is the date of first administration of study treatment during the study as recorded in eCRF (Dosage Administration Record summary page).

**Date of last study treatment ("last dose date" or "LDDT")** is the date of last administration of study treatment during the study as recorded in eCRF (Dosage Administration Record summary page).

Study day is number of days counted from the first dose date (Day 1).

For dates on or after FDDT, study day = date of interest - FDDT + 1.

For dates prior to FDDT, study day = date of interest – FDDT.

If first dose date is missing, the randomization date will instead be used for the calculation.

**Baseline** for analysis, in general, is the last assessment with valid data before the date and time of first administration of study treatment. If the date of assessment is the same as first dose date but time is not available for comparison, the assessment is assumed to be prior to the administration of study treatment. For ALT, AST, ALP, GGT and total bilirubin, however, the baseline is the average of values from two screening visits and the baseline visit collected before first administration of study treatment. If there is unscheduled visit with lab assessment after a planned screening visit, the value from this unscheduled visit will also be used in the calculation of baseline.

End of study (EoS) or last contact date of a patient is the date of his/her last office visit or other route of follow-up in the study.

**Treatment period** is the period from the Baseline visit (included) to the TD/EOT (W48) visit (included) as defined in protocol Table 8-1.

Follow-up period is the period from TD/EOT (W48) visit (not included) to EoS (included).

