**Analysis visit** is the visit label derived based on study day of assessment and the analysis visit windows defined in Table 2-1. For laboratory and bioanalytical parameters specified for both Group 1 and Group 2 in Table 2-1, two sets of analysis visits will be derived and will be referred to as "**AV1**" and "**AV2**" respectively. The AV1 is derived according to Group 1 for by visit analysis on full analysis set (FAS). For AV2, assessments >14 days after the last dose date will be slotted into the analysis visit window for follow up visit for by-visit analysis of laboratory data on safety analysis set (SAF).

**Analysis visit windows** are non-overlapping periods each associated with a visit planned in protocol and all together cover the entire study period of a patient. If multiple measurements of same parameter for a patient fall in the same window, the value of this analysis visit is selected according to Table 2-2. If no assessment falls into a window, the value of that analysis visit will be set to missing unless imputation rule(s) are defined for the parameter. Repeat and unscheduled visits will be mapped to analysis visits in the same way as scheduled visits.

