# 2.4.1 Study treatment / compliance

The duration of exposure (days) to study treatment will be calculated as the LDDT – FDDT +1 and summarized by study treatment. In addition, the number (%) of patients with LDDT in the following time intervals after FDDT will be summarized by study treatment:

- <4 weeks
- $\geq 4$  and < 8 weeks
- $\geq 8$  and < 12 weeks
- $\geq$  12 and < 16 weeks
- $\geq 16$  and < 20 weeks
- $\geq 20$  and < 24 weeks
- $\geq$  24 and < 32 weeks
- $\geq$  32 and < 40 weeks
- $\ge 40$  and < 48 weeks
- $\geq$  48 weeks

The proportion of patients with dose reduction (including interruption) due to adverse event, as recorded in the change in dosing log CRF page, will be presented by study treatment.

Dose intensity is derived as the ratio between the cumulative dose of each active ingredient (tropifexor and licogliflozin) received during the study and duration of exposure (days). Patients in combination arm will have dose intensities derived separately for tropifexor and licogliflozin.

The relative dose intensity (compliance) is derived as the ratio between the actual dose intensity and the planned dose intensity which equals to the actual duration of exposure \* the daily dose of tropifexor or licogliflozin as planned according to protocol.

Number (%) of patients incompliant with planned regimen, defined as relative dose intensity >1.25 or <0.75, will be summarized for tropifexor in the LJN452 monotherapy arm, for licogliflozin in the LIK066 monotherapy arm, and for both tropifexor and licogliflozin separately in the combination arm.

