# 2.8 Safety analyses

All safety analyses will be on SAF and presented by study treatment actually received (Section 2.2).

If not clarified otherwise, safety summaries will include only data from the on-treatment period except that baseline data may also be summarized where appropriate (e.g. change from baseline summaries). The on-treatment period lasts from the date of first administration of study treatment to 30 days after the date of the last dose date.

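### SAP 5.1.1 can default a missing last dose date to Day 1 although later dosing is on record, which understates exposure and cuts short the on-treatment safety window

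*SAP*

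**What the plan says.** SAP 2.1.1 takes the last dose date from the Dosage Administration Record summary page; it "is the date of last administration of study treatment during the study". SAP 5.1.1 covers the case where that field is empty but the first dose date is known, with loss to follow-up as its example. The missing date "will be imputed with patient's first dose date or the last known exposure to study treatment according to change in dosing CRF page", taking the later of the two. It names no other source.

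The documents show two uses of the change-in-dosing page. SAP 2.4.1 counts dose reductions, including interruptions, due to adverse events "as recorded in the change in dosing log CRF page". Protocol 6.7.2 asks that the date of the move from three capsules to one "is accurately captured in the eCRF Change in Dosing log for each participant".

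The last dose date then enters three derivations:
- Exposure (SAP 2.4.1) is last dose date minus first dose date plus 1.
- The safety window (SAP 2.8): "The on-treatment period lasts from the date of first administration of study treatment to 30 days after the date of the last dose date".
- By-visit laboratory summaries (SAP 2.1.1, the AV2 visits): "assessments >14 days after the last dose date will be slotted into the analysis visit window for follow up visit".

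Other dosing evidence is collected. Protocol 8.2.7 states: "All doses of study treatment administration will be recorded on the appropriate eCRF page". Protocol Table 8-1 marks the drug administration record from Baseline to Week 40, and drug compliance from Week 2 to Week 40, as data for the clinical database.

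**The concern.** An imputation rule for a last dose date should estimate when dosing stopped. This one looks only at a page that, as described, has an entry when dosing changes. A participant who took the drug steadily and then stopped attending may have no such entry, and the rule then returns the first dose date even though later visits documented dosing. Uninterrupted participants are the ones most exposed to it.

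The error has a direction: exposure is understated and the on-treatment window is too short. Safety and tolerability over 48 weeks is a stated secondary objective. Protocol 12.5.2 ends the on-treatment period 30 days after the last actual administration, and a Day 1 default does not estimate that date when later intake is on record. SAP 4.12 also drops the listings of pre- and post-treatment safety data, so events pushed outside the window would not reappear in a formal post-treatment listing.

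**Working it through.** The plan gives no figure to reproduce, so the SAP date rules are applied to one case.

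**Inputs**
- First dose = Day 1 (SAP 2.1.1).
- Post-baseline target days from SAP Table 2-1: Weeks 2, 4, 8, 12, 16, 20, 24, 32 and 40 fall on Days 15, 29, 57, 85, 113, 141, 169, 225 and 281. That is nine visits, each at 7 × week + 1.
- Assumed case: last seen and truly dosed on Day 281, with the last dose date missing from the summary page.

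**Formulas** (L = last dose day)
- Exposure = L − 1 + 1 = L days.
- On-treatment window ends on Day L + 30.
- AV2 relabels as follow-up any assessment after Day L + 14.

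**No later entry on the change-in-dosing page, so L = 1**
- Exposure = 1 day, which falls in the under-4-weeks category. The true value is 281 days.
- Window ends on Day 1 + 30 = 31 instead of 281 + 30 = 311. Observed days outside it: 281 − 31 = 250, and 250/281 = 89%. Only Weeks 2 and 4 fall inside; the other seven visits fall outside.
- AV2 cut-off is Day 1 + 14 = 15 instead of 281 + 14 = 295. Week 2 (Day 15) keeps its label. Weeks 4 to 40 do not: 8 of 9 are relabelled.

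**A later entry softens this**

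| Imputed last dose | Exposure | Window ends | Observed days outside | Laboratory visits relabelled |
|---|---|---|---|---|
| Day 1 | 1 | Day 31 | 250/281 = 89% | 8 of 9 |
| Day 85 | 85 | Day 115 | 166/281 = 59% | 5 of 9 |
| Day 169 | 169 | Day 199 | 82/281 = 29% | 2 of 9 |
| Day 281 (true) | 281 | Day 311 | 0 | 0 of 9 |

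**Outputs that do not depend on the last dose date.** SAP 2.8.3 uses all post-treatment data, whatever the last dose date, for shift tables, hepatotoxicity and nephrotoxicity events and other notable laboratory abnormalities. SAP 2.8.2 lists deaths at any time in the study.

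**Adverse events.** SAP 2.8.1 defines a new treatment-emergent event by its start after first dose and sets no end limit. SAP 2.8 restricts safety summaries to on-treatment data unless clarified otherwise. I read 2.8 as governing, in which case events starting after Day 31 are lost from these summaries.

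**Scale across the trial.** The documents give no rate of missing last dose dates. If 1%, 3% or 5% of the 380 planned participants were affected, that is about 4, 11 or 19 people. In the worst case each loses 281 − 1 = 280 days. Against 380 × 336 = 127,680 planned days, the loss is 1,064, 3,192 or 5,320 days, or 0.8%, 2.5% or 4.2%. These rates are assumptions.

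**The case against.** The strongest reply is that the rule may seldom fire. It needs a last dose date still missing from the dosing summary page, while administration is recorded at visits through Week 40 and Protocol 11.2 provides for queries on missing values. A reader might infer that anyone lost at Week 40 is analysed as exposed for one day. The documents do not support that: loss to follow-up alone does not trigger the rule. The SAP does, however, anticipate the situation and names loss to follow-up as its example.

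Second, the eCRF is not among the documents, and no text says the change-in-dosing page holds changes only. If it carries dosing intervals, the Day 1 result would not arise. This stands as a limit; the result rests on the two uses the documents do describe.

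Third, a reader might infer that nearly all of the participant's safety data are lost. That is too strong. The exempt outputs in SAP 2.8.2 and 2.8.3 remain, AV2 relabels laboratory values without deleting them, the disclosure tables are planned for the overall study period, and the adverse-event loss depends on how 2.8 and 2.8.1 are read together.

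Fourth, a reader might extend the problem to histology through the condition of at least 24 weeks of treatment in SAP 2.5. That condition matters only for someone who had a biopsy after 24 weeks, and so attended a late visit. Nothing shows that such a person would also lack a last dose date, or ties the condition to the imputed date.

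Finally, the SAP predates the current protocol (it was written for 210 patients) and foresees amendment. That makes the correction easy but does not remove the rule.

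**Conclusion.** The point holds in a limited form. When the last dose date is missing and the change-in-dosing page has no later entry, following SAP 5.1.1 gives a wrong date although the database should hold better evidence. For a participant truly dosed to Day 281, exposure is understated by 280 days, 89% of observed days leave the on-treatment window, and 8 of 9 by-visit laboratory assessments move to follow-up.

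This assumes that the page is as the documents describe it and, for adverse events, that SAP 2.8 bounds the treatment-emergent summaries. The number affected is unknown. Applying a loss-to-follow-up rate, or the roughly 10% dropout in SAP 3.1, would not give it, because neither is a rate of missing last dose dates. The consequence is for exposure and safety reporting; no effect on the primary endpoint is shown. The rule should be corrected because it errs in a known direction and the remedy is cheap.

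**What to change.** Replace the sentence in SAP 5.1.1. Impute a missing last dose date as the latest administration documented in the clinical database: the last visit at which the drug administration record or the compliance data show intake, or the change-in-dosing page if later. Cap it at the last contact date defined in SAP 2.1.1. Use the first dose date only when there is no later evidence of intake.

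The rule should not rely on diaries or raw pill counts. Table 8-1 marks diary review as source documentation only, and Protocol 6.6.1 places pill-count information in the source document, so using them could require new data entry.

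The cost is one SAP sentence and a small derivation change, with no new data, best made before database lock and unblinding. The imputed date remains approximate and may slightly overstate or understate true exposure. The same revision could state whether the SAP 2.8 window bounds new events under SAP 2.8.1.

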#### 5.1.2 AE start and stop dates

#### **AE Start Date Imputation:**

AE start date with missing year or with missing month but non-missing day will be resolved through data queries.

Defining AE reference date as

- If AE end date (after imputation if needed) <= first dose date, AE reference date = min (informed consent date, earliest visit date of SVs)
- Else AE reference date = first dose date

and following date components

	Day	Month	Year
Partial AE Start Date		MON	YYYY
AE reference Date	REFD	REFM	REFY

incomplete AE start date will be inputted according to logic matrix

(Imputation)	MON MISSING	MON < TRTM	MON = TRTM	MON > TRTM
YYYY MISSING	NC	NC	NC	NC
YYYY < TRTY	(D)	(C)	(C)	(C)
YYYY = TRTY	(B)	(C)	(B)	(A)
YYYY > TRTY	(E)	(A)	(A)	(A)

where

NC	No convention - require data query
(A)	01-MON-YYYY
(B)	AE reference date
(C)	Last day of month MON-YYYY
(D)	Last day of year YYYY
(E)	01-JAN-YYYY

Novartis	
SAP	

The algorithms will be reflected in the Variable Source Derivation column as #IMPUTAEV (*event*) where *event* is the incomplete start date of the adverse event.

#### **AE End Date Imputation:**

If all AE end date components are missing after data queries, the AE is considered ongoing for analysis purpose.

If AE end month is missing, the AE end date is imputed as the last day of AE end year or patient's study completion/discontinuation visit date, whichever is earlier.

If AE day is missing, then AE end date is imputed as the last day of the month or patient's study completion/discontinuation visit date, whichever is earlier.

If imputed AE end date is less than the AE start date, use the AE start date as the imputed AE end date.

#### Impute Date Flag:

If year of the imputed date  $\neq$  YYYY then date flag = Y

else if month of the imputed date  $\neq$  MON then date flag = M

else if day of the imputed date  $\neq$  day of original date then date\_flag =

D else date flag = null

# 5.1.3 Start and stop dates of prior/concomitant medications or non-drug therapies / procedures

The imputation for incomplete start or stop date of medications or non-drug therapies / procedures patients received in addition to study treatment during the study will follow the same algorithms for imputations of incomplete AE start/stop date.

